3.3.3 Ancillary Safety Outcome Measures

We will report all adverse and serious adverse events for both study groups as described in the investigators brochure guide.⁴ In addition, we will run an immunoglobulin panel in the switching group as well.

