4.1.2 Inclusion Criteria

Switching group:

- Current active patient of RMMSC
- 18-65 years
- Diagnosis of relapsing forms of MS
- Completed **≥ two doses** of rituximab with the last dose having been administered:
 - a) within 12 months of screening
 - and
 - b) at least 6 months prior to first planned infusion of study drug
- Are receiving their current infusions of rituximab at the University of Colorado Outpatient Infusion Center
- Have discussed the possibility of switching to ocrelizumab with their MS provider
- Screened for Hepatitis B and C and TB within 2 years of first dose of ocrelizumab
- A negative serum pregnancy test must be available for premenopausal women and for women <12 months after the onset of menopause, unless they have undergone surgical sterilization.
- Women of childbearing potential must agree to use a “highly effective”, hormonal form of contraception or two “effective” forms of non-hormonal contraception. Contraception must continue for the duration of study treatment and for at least three months after the last dose of study treatment
- Are able to complete patient reported outcomes developed as English written scales.
- Must be able and willing to give meaningful, written informed consent prior to participation in the trial, in accordance with local regulatory requirements

Comparator group:

- Current active patient of RMMSC

- 18-65 years
- Diagnosis of relapsing forms of MS
- Completed \geq **two doses** of rituximab with the last dose having been administered within 12 months of screening as standard of care
- Are receiving their current infusions of rituximab as standard of care at the University of Colorado Outpatient Infusion Center and will continue to do so
- Are willing to be followed for subsequent rituximab infusions during the study period as standard of care, and/or allow retrospective data collection on previous rituximab infusions
- Must be able and willing to give meaningful, written informed consent prior to participation in the trial, in accordance with local regulatory requirements

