4.5.1 Assessments during Treatment

The following evaluations will be conducted during and post treatment:

Study Visits and Procedures Summary:

Study visits for the switching group include a) screening visit, b) first infusion of 300 mg of ocrelizumab (day 1 or T₀), c) 300 mg of ocrelizumab infusion on day 15 (T₁), d) 600 mg of ocrelizumab at 6 months (+/- 2 weeks) after day 1 (T₂) and, e) a research termination visit between month 12 and 18 - (+/- 2 weeks)(T₃). In some cases, screening procedures may be performed on the first infusion day rather than as a separate visit. The patient may continue on 600 mg of ocrelizumab or (if the patient prefers) 500mg rituximab at T₃, or 12 to 18 months after Day 1 (T₀). A month is defined as 28 days. Study visits for the comparator group include only standard of care infusion of rituximab, up to two infusions per patient, approximately 6 months apart. Research data on IRRs for the comparator group will be collected from the medical records.

A summary of all procedures for switching group is outlined under “Schedule of Events” in **Table 1** below. During the screening visit, patients will be consented for the study and receive both a medical and full neurological exam. Verification of their hepatitis B and C status including testing will be conducted if a patient has not been tested in the last two years. MS disease history and demographic information will also be collected. Patients will also receive an EDSS exam and take an online version of the PDDS (done as standard of care- on an iPad).

The Expanded Disability Status Scale (EDSS) is a commonly used assessment that allows clinicians to objectively measure changes in the disability status of MS patients using unbiased clinical raters.⁷ The **EDSS** provides a total score on a scale that ranges from 0 to 10. The first levels 1.0 to 4.5 refer to people with a high degree of ambulatory ability and the subsequent levels 5.0 to 9.5 refer to the loss of ambulatory ability. The range of main categories include (0) = *normal neurologic exam*; to (5) = *ambulatory without aid or rest for 200 meters; disability severe enough to impair full daily activities*; to (10) = *death due to MS*. In addition, it also provides seven subscale measurements called Functional System (FS) scores.

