(generalized linear mixed models) methods to incorporate correlation on repeated infusions on a patient. The same method will apply to other longitudinal binary outcomes. Poisson or negative binomial models with exposure terms could calculate rates of IRR per infusion per patient as a counting process. Similar methods will be used to compare IRR rates between the switching group and OPERA I and II phase 3 clinical trials. The total number of IRRs experienced in each patient, will be analyzed with Poisson or negative binomial models. Paired T tests will be used to assess differences in specific cytokine markers between pre and post infusion at each infusion cycle. Patient reported outcomes will also be reported descriptively. Frequencies and proportions will be reported for adverse and serious events and loss to follow up

As contingency methodology, exact tests and confidence intervals for measures of association between categorical variables can be utilized when necessary, if the sample sizes for some of the cells are small. Transforms or rank based methods, such as Wilcoxon sign rank, can be used in place of the T-test if deviation for normality is severe. Otherwise the T-test is a robust test of mean differences for medium to large sample sizes. If matching leads to good balance between the treatment groups on the demographic and disease variables, including age, MS disease duration, and baseline PDDS score, then confounding will not be an issue and the proposed unadjusted tests should be adequate. Alternatively, if the demographic and disease variables are not balanced, then regression or propensity score methods will be used to adjust for potential confounding. Sensitivity analysis comparing unadjusted and adjusted results will be used to determine the extent of the confounding effect. Adjustment for covariates can sometimes improve the precision of the estimated treatment difference by reducing random noise in the outcome.

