5. REPORTING OF ADVERSE EVENTS

5.1 Assessment of Safety

Safety Review

All AEs and SAEs will be reviewed by the project Steering Committee at their monthly project management meetings. This Committee will be composed of Drs. [name], [name] and [name] supported by [name] PhD and the lead study coordinator, [name]. We will also establish an external DSMB as required by UCD that will meet at baseline, then every 6 months and at the time of any SAE. This committee will consist of two neurologists and [name] PhD biostatistics.

Adverse Events

An AE is any unfavorable and unintended sign, symptom, or disease temporally associated with the use of an investigational medicinal product (IMP) or other

protocol-imposed intervention, regardless of attribution. For the patients on Ocrelizumab, all AEs occurring between the time of consent and the study termination visit will be recorded.

For the comparator group, IRRs are the only AEs that will be collected. In addition, clinical relapses documented during the clinical process will also be collected.

Serious Adverse Events

An AE should be classified as an SAE if the following criteria are met:

- It results in death (i.e., the AE actually causes or leads to death).
- It is life threatening (i.e., the AE, in the view of the investigator, places the subject at immediate risk of death. It does not include an AE that, had it occurred in a more severe form, might have caused death.).
- It requires or prolongs inpatient hospitalization.
- It results in persistent or significant disability/incapacity (i.e., the AE results in substantial disruption of the subject's ability to conduct normal life functions).
- It results in a congenital anomaly/birth defect in a neonate/infant born to a mother exposed to the IMP.
- It is considered a significant medical event by the investigator based on medical judgment (e.g., may jeopardize the subject or may require medical/surgical intervention to prevent one of the outcomes listed above).

All SAEs reported or observed in either group will be recorded and reported as necessary.

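### Crude SAE proportions will not be comparable between the groups: comparators have no defined SAE observation period and the plan has no person-time or common-window measure

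*Combined protocol and SAP*

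**What the plan says.** **Reporting.** Section 3.3.3 states "We will report all adverse and serious adverse events for both study groups", and section 5.1 states "All SAEs reported or observed in either group will be recorded and reported as necessary". Section 4.9.4 gives the summary measure: "Frequencies and proportions will be reported for adverse and serious events and loss to follow up". The same section mentions exposure terms only for models of infusion-related reactions (IRRs).

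**Switching group.** Section 5.1: "For the patients on Ocrelizumab, all AEs occurring between the time of consent and the study termination visit will be recorded". Section 4.5.1 places the end of that period at "a research termination visit between month 12 and 18" and defines a month as 28 days. Section 5.2 instead puts T3 six months after the last dose.

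**Comparator group.** Section 4.5.1 limits visits to standard-of-care rituximab infusions, "up to two infusions per patient, approximately 6 months apart". Section 4.1.2 admits patients who will be followed prospectively "and/or allow retrospective data collection on previous rituximab infusions", and section 3.1 describes the retrospective data as IRR data. Section 5.1 also says "For the comparator group, IRRs are the only AEs that will be collected", then adds relapses and, further on, SAEs in either group. The reporting period in section 5.2 begins after consent and ends at T3, a visit that comparators do not have.

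**Scope.** Section 2.2 lists the description of adverse and serious adverse events among objectives assessed in the switching group only, which conflicts with sections 3.3.3 and 5.1.

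**The concern.** The proportion of patients with at least one SAE rises with the length of observation. If one group is watched for about a year or more and the other for a shorter or unstated time, the two percentages differ even when the drugs carry the same risk.

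For comparators, the only safety data beyond IRRs are SAEs and documented relapses, so the SAE table is the main non-IRR safety comparison the study can offer. The study is meant to inform decisions about switching. A table with a visibly higher SAE percentage on ocrelizumab could be read as a safety signal although no test was run. The missing comparator window also leaves the analyst to choose it after the data are in, and that choice moves the result.

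**Working it through.** **The plan's own figures.** The documents give no SAE rate, SAE person-time or SAE power to reproduce. Their only power figure is 90% for IRRs (14.3% against 34.3%, 95 patients per group, two-sided 5%). It reproduces at 0.901 but has no bearing on SAEs.

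**Inputs from the documents**
- Switchers, T3 at month 12 to 18 (4.5.1): 12 × 28/7 = 48 weeks and 18 × 28/7 = 72 weeks after Day 1. Under the wording of 5.2, with T2 at month 6, T3 falls at month 12, or 48 weeks.
- Comparators, two infusions 6 months apart (4.5.1): 6 × 28/7 = 24 weeks from first to last infusion. This is a visit span, not a stated SAE window.
- Infusions per comparator (4.1): 200 infusions from 100 to 200 patients, so on average 2 down to 1 each. A one-infusion patient has a span of 0.

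**Assumptions not in the documents**
- A constant SAE rate, equal in both groups, of 2, 5 or 10 per 100 patient-years.
- Comparator observation of 24 weeks (the visit span) or 48 weeks (record review to 6 months after a second infusion, by analogy with 5.2).

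**Formula.** P(at least one SAE) = 1 − exp(−rate × weeks/52.18).

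**At 5 per 100 patient-years**
- 24 weeks: 1 − exp(−0.05 × 24/52.18) = 2.27%
- 48 weeks: 1 − exp(−0.05 × 48/52.18) = 4.50%
- 72 weeks: 1 − exp(−0.05 × 72/52.18) = 6.67%

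**Ratio of switcher to comparator percentage, with no true difference**

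| Assumed rate per 100 patient-years | Comparators 24 weeks | Comparators 48 weeks |
|---|---|---|
| 2 | 1.99 to 2.97 | 1.00 to 1.49 |
| 5 | 1.98 to 2.93 | 1.00 to 1.48 |
| 10 | 1.96 to 2.87 | 1.00 to 1.47 |

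The lower end of each range is T3 at 48 weeks, the upper end T3 at 72 weeks. The assumed rate hardly matters: for uncommon events the ratio is close to the ratio of the windows (48/24 = 2, 72/24 = 3, 48/48 = 1, 72/48 = 1.5).

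**Retrospective-only comparators.** If a share r of comparators has no SAE time but stays in the denominator, the ratio is divided by (1 − r). The documents do not give r. For illustration at r = 25% and 5 per 100 patient-years, the ratio is 2.64 to 3.91 with 24 comparator weeks and 1.33 to 1.98 with 48.

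**With the remedy.** A rate per patient-year, or the same window in both groups, gives an expected ratio of 1.0 at equal risk.

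**The case against.** **No between-group SAE comparison is really planned.** The sentence in 4.9.4 does not say by group, section 2.2 confines AE and SAE description to switchers, SAEs are not among the secondary endpoints in 4.9.4, and no SAE test is specified. This stands as a reason for low severity. It does not remove the point, because 3.3.3 and 5.1 do call for SAEs in both groups, and the sections contradict each other.

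**The protocol already urges caution.** Section 4.2 says events are collected by different methods in the two groups and that differences in incidence will be of limited interpretability. That is a fair defence, but it concerns collection method and does not mention unequal observation time.

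**The comparator window is not known to be short.** Section 5.2 allows SAEs to come from medical records, and 4.5.2 leaves comparator follow-up to standard care. This stands. A reader might infer from the visit schedule that comparators are observed for 24 weeks and that a two- to threefold excess on ocrelizumab must follow. The documents do not say so: with 48 weeks of record review the ratio is 1.0 to 1.5.

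**Zero-time patients may not be counted.** Section 4.9.4 sets an available-case default, which could be read as leaving out patients without SAE observation. Section 4.1, however, includes all patients in the analyses, so the denominator is unsettled.

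**Conclusion.** The concern holds as a gap in definition. The plan calls for SAE reporting in both groups, summarises SAEs as crude frequencies and proportions, and states no comparator SAE period. Group percentages produced this way are not comparable and probably overstate SAEs on ocrelizumab.

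At equal risk the distortion runs from none to about 1.5-fold with 48 comparator weeks, and is about 2- to 3-fold with 24. It rests on a constant, equal SAE rate and on comparator windows that are assumed. The direction would change only if comparators were observed for longer than switchers, which nothing in the text suggests.

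A reader might go further and infer a four- to sixfold excess. That needs 24 comparator weeks, half of the comparators to be retrospective-only, and all of those kept in the denominator. The documents give no such share and do not settle the denominator, so this figure is not supported.

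Severity is low: the table is ancillary, descriptive and untested.

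**What to change.** In section 4.9.4:
1. Define the comparator SAE period. Start at consent, as for switchers in 5.1, and state an end, such as a dated final record review.
2. Report SAEs by group as events, and patients with an event, per patient-year of prospective observation, with confidence intervals. Alternatively, tabulate both groups over one common window after the first prospective infusion.
3. Exclude retrospective-only comparators from the SAE denominator and report their number.
4. Use the start and stop dates to assign SAEs for patients who contribute to both groups, as 4.1 permits.
5. Keep the caveat in 4.2. Person-time corrects for length of observation but not for the difference between asking switchers at visits and reading comparators' charts.

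Reconcile three conflicts: section 2.2 (switching group only) with 3.3.3 and 5.1 (both groups); the statement in 5.1 that IRRs are the only comparator AEs with its later SAE sentence; and the T3 timing in 4.5.1 with that in 5.2.

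The cost is SAP wording, two dates per patient, and a record review for SAEs in comparators, since 4.5.1 and 4.5.2 describe record collection only for IRRs. The SAE table will hold fewer comparators and its intervals will be wider.

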Safety data from the Investigators Brochure on the OPERA I and II phase 3 trials comparing ocrelizumab to interferon β -1a on relapsing MS patients showed that IRRs were the most common adverse events experienced by patients treated with 600 mg of ocrelizumab.⁴ The percentage of patients experiencing IRRs was higher in the ocrelizumab group (relapsing forms of MS: 34.3%; primary progressive forms of MS 39.9%) compared with the interferon β -1a (active control) group who received placebo infusions (relapsing forms of MS: 9.7%; primary progressive forms of MS: 25.5%). The rate of IRRs was highest during the first infusion or Dose 1 (27.5% on Day 1; 4.71% on Day 15 of Dose 1) and decreased over time (13.7%; 9.6% and 7.8% following Dose 2, 3, and 4 respectively) for the ocrelizumab treated group. Comparatively, interferon β -1a users experienced 6.5% of IRRs on Day 1, 2.58% on Day 15, \leq 2.00% after doses 2, 3 and 4 respectively. The reported IRRs were primarily mild-to-moderate in severity (Grades 1 and 2). Serious IRRs occurred in 0.1% and 1.0% respectively of relapsing and progressive patients and treated with ocrelizumab.

Clinical data describing the efficacy and tolerability profile of rituximab and ocrelizumab has utilized populations with different prior treatment characteristics. In the phase 2 HERMES trials, a majority (78.5%) of rituximab patients had been **previously been treated** with a disease modifying therapy in the last 2 years.³ In contrast, the OPERA I and II phase 3 clinical trials, a majority of ocrelizumab

patients (72.9% in OPERA I and 73.8% in OPERA II) represented a **treatment naïve population**.⁴ Examining IRRs in patients who have switched from rituximab to ocrelizumab versus those continuing on rituximab will evaluate the magnitude of the IRRs and subsequent tolerability of ocrelizumab in a real world population of MS patients previously been exposed to rituximab.

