4.2 Method of Treatment Assignment

The study will not be a randomized trial. Patients will not be assigned to the switching group, but rather will be enrolled after a clinical decision has been made with their provider about whether they will continue on rituximab or switch

to ocrelizumab. The following steps will be taken to minimize potential biases in sample selection.

First, in an effort to impose some degree of similarity between the treatment groups, control patients will be matched, either 1:1 or 2:1 depending on the number of control patients, with switching patients on gender and age (+/- 2 years) at recruitment. The demographic information on switching patients will be scanned to find matches for the patients in the non-switching group.

Furthermore, screening of additional patients beyond the 200 required for enrollment in the non-switching group will be also conducted to ensure the best possible matches. Second, baseline statistics will be monitored as patients enter the study, and selection of patients may be modified in order to maintain relative balance between treatment groups (if necessary using measures of disease severity other than age and gender) if we are able to overenroll the number of non-switchers. Third, demographic variables and measures of baseline disease severity, including age, gender, MS disease duration, type of MS at baseline (first infusion in both study groups), along with discontinuations, will be recorded and compared between treatment groups.

All available observations will be used. For continuous variables (age, MS disease duration), by treatment group means, standard deviations, medians, and ranges will be recorded, and differences among treatment groups will be tested for with either with T-test/ANOVA methods or Wilcoxon/Kruskal Wallis tests. For categorical variables (gender, type of MS, disability, discontinuations), frequencies and proportions will be presented, and differences among treatment groups will be tested for using chi-square/Fisher's exact test. Fourth, following these measures, if treatment confounding is found to still be an issue, regression or propensity score methods, with covariates such as age, MS disease duration, and baseline EDSS score will be used post hoc to minimize confounding.

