4.9.6 Determination of Sample Size

The sample size will be a convenience sample. It is anticipated a minimum of 100 patients will qualify for each cohort (200 total) resulting in studying 300 infusions with ocrelizumab and 200 infusions with rituximab. This is an observational study not designed to demonstrate superiority of ocrelizumab over rituximab in efficacy but instead indicate the magnitude of the relative tolerability and immunogenicity. The primary endpoint is the difference in the percentage of IRRs between the two study groups. In addition, both study groups will include treatment experienced patients on rituximab who have experienced a minimum of two infusions and either continue to stay on rituximab or switch to ocrelizumab.

To estimate study power with the proposed sample size of 100 infusions in each group, we conducted a chart review of 50 patients at the Rocky Mountain MS Center who are currently taking rituximab and examined their IRRs using the proposed IRR grading scale (see section 3.3.1) from Grade 0-5. The number and severity of IRRs were captured following their third rituximab infusion. The highest grade of an IRR that occurred during the infusion was recorded. Our pilot data revealed that following the third rituximab infusion, 14.3% of patients had an IRR of which 85.71% were Grade 0, 12.24% were grade 2 and 2.05% were Grade 3. Hauser et al., found that following the second infusion of rituximab in patients, the majority of whom (60%) were not taking a DMT for 6 months prior to initiating rituximab only 20.3% experienced in an IRR.³

Using IRR estimates from our pilot data and establishing a clinically meaningful difference of 20% increase in IRRs, we conducted the following power analysis for a sample of 95 patients (assuming a 5% attrition rate after recruiting 100 patients in each study group). An IRR proportion for ocrelizumab users at 34.3% compared with 14.3% for rituximab (obtained from our pilot data) for a two sided (alpha = 0.05) two sample proportion test for the null hypothesis of no difference between rituximab and ocrelizumab in proportion of IRRs would result in 90% power for 95 patients per group.

In response to the FDA IND letter, “the power analysis in Section 4.9.6 of the protocol appears to compare the infusion-related reaction (IRR) rate at the third rituximab infusion (14.3%) to that of the first infusion of OCR (34.3%). Because

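### Adjustment of the non-randomised primary IRR comparison depends on balance in demographic and disease variables, and prior anti-CD20 exposure is not among them

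*Combined protocol and SAP*

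**What the plan says.** Section 4.2 states that there is no randomisation. Group follows a decision between patient and provider, and comparators are matched to switchers on gender and age within two years. Sections 4.2 and 4.9.2 list what is compared at baseline: age, gender, MS duration, type of MS, disability (PDDS in 4.9.2) and discontinuations. The comparison uses significance tests.

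Section 4.9.4 sets the rule for the primary analysis: "If matching leads to good balance between the treatment groups on the demographic and disease variables", "then confounding will not be an issue and the proposed unadjusted tests should be adequate". If those variables are not balanced, regression or propensity scores are used. No balance threshold is given. Section 4.2 has the same trigger but names a different disability scale: "covariates such as age, MS disease duration, and baseline EDSS score will be used post hoc to minimize confounding".

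Section 4.9.4 also promises a sensitivity analysis of unadjusted against adjusted results, without naming covariates. Section 4.5.1 says that PDDS will serve to characterise and control for disability in both groups.

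On infusion order, the introduction reports that ocrelizumab IRRs were 27.5% on Day 1 and "decreased over time (13.7%; 9.6% and 7.8% following Dose 2, 3, and 4 respectively". It reports rituximab IRRs of 78.3% at the first infusion and 20.3% at the second in the phase 2 trial. The agency comment reproduced in section 4.9.6 makes the same general point about monoclonal antibodies.

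**The concern.** Balance on measured demographic and disease variables says nothing about variables that were not examined. The documents do not link age, MS duration or disability to IRR risk, but they do link infusion order to it. Yet number of prior infusions, time since the last one and prior IRRs appear in no matching, balance or adjustment list. A comparison could pass every listed check and still differ in infusion history.

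The documents leave several routes open for such a difference:

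- Eligibility (4.1.2) sets a floor of two prior rituximab doses and no ceiling.
- Only switchers must be at least six months from their last rituximab dose at the first study infusion.
- Sections 3.1 and 4.1.2 allow comparator infusions to be collected back to August 2016. No text excludes a patient's first or second infusion.
- Section 4.1 lets a comparator patient enter the switching group later, by then with more prior exposure if infused in between.
- Section 3.2 says that ocrelizumab's positioning as possibly better on IRRs will influence some patients and prescribers.

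What is at stake is whether the primary difference reflects the drug or the infusion history. A confidence interval from the unadjusted test would not show which.

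**Working it through.** **1. The plan's own figure.** Inputs from section 4.9.6: "An IRR proportion for ocrelizumab users at 34.3% compared with 14.3% for rituximab", "for a two sided (alpha = 0.05) two sample proportion test", "would result in 90% power for 95 patients per group". With pooled variance under the null, power = Φ[(d − 1.96·√(2p̄(1−p̄)/n)) / √((p1q1 + p2q2)/n)].

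- d = 0.200, p̄ = 0.243, n = 95.
- √(2 × 0.243 × 0.757 / 95) = 0.0622, and × 1.96 = 0.1220.
- √((0.2254 + 0.1226)/95) = 0.0605.
- (0.200 − 0.1220)/0.0605 = 1.289, so power = 90.1%.

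The stated 90% reproduces. It assumes a comparison free of confounding.

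**2. Size of the infusion-order effect within the eligible window.** Section 4.1.2 requires two completed rituximab doses, and section 2.1 describes them as at least six months apart. Section 4.9.6 places the first study infusion at the third anti-CD20 infusion or later. Counted in six-monthly courses, the relevant step in the introduction is Dose 3 to Dose 4: 9.6 − 7.8 = 1.8 points, or 1.8/20 = 9% of the target difference. No rate is given beyond Dose 4.

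**3. If early comparator infusions enter.** Assume that a share s of comparator infusions are first rituximab infusions at 78.3% (introduction) and the rest run at the pilot 14.3% (section 4.9.6). The documents do not give s.

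- s = 5%: 0.05 × 78.3 + 0.95 × 14.3 = 17.5%, a rise of 3.2 points.
- s = 10%: 0.10 × 78.3 + 0.90 × 14.3 = 20.7%, a rise of 6.4 points.

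With ocrelizumab held at 34.3%, the formula in step 1 gives power of 76% and 56%. Here confounding hides part of a true difference.

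**4. An omitted driver with no true drug effect.** All values here are assumptions except the 14.3% comparator rate. The driver has prevalence 30% in comparators, prevalence π in switchers, and relative risk R for an IRR. Base rate b = 0.143/(0.7 + 0.3R); switcher rate = b(1 − π + πR).

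| R | π | Switcher rate | Spurious difference | Unadjusted test rejects (nominal 5%) |
|---|---|---|---|---|
| 1.5 | 40% | 14.9% | 0.6 points | 5.2% |
| 3 | 50% | 17.9% | 3.6 points | 10.3% |
| 4 | 60% | 21.1% | 6.8 points | 23.1% |

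**5. Balance tests on the listed covariates.** This is a separate matter from steps 2 to 4. Taking a 0.05-level test as the criterion, a standardised imbalance of 0.2 or 0.3 is detected with 28% or 54% power at 95 per group, and with 37% or 69% at 100 against 200. A non-significant test is therefore weak evidence of balance even for the variables it covers.

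**The case against.** The plan is less bare than a quick reading suggests. The list in 4.9.4 is open-ended, and 4.9.2 adds gender and type of MS. Section 4.2 lets patient selection be modified to keep balance, the sensitivity analysis may produce an adjusted result even when balance looks good, and 4.5.1 intends PDDS as a control variable. All of that stands, but none of it brings in infusion history. The sensitivity analysis has no stated covariates and does not replace the primary result.

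Some stronger readings are not supported:

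- A reader might take the step from Dose 2 (13.7 − 9.6 = 4.1 or 13.7 − 7.8 = 5.9 points) and conclude that 20 to 30% of the target could be confounding. Counted in courses, Dose 2 lies below the exposure floor for prospective infusions. The rates are also ocrelizumab after ocrelizumab, in a population described as mostly treatment naive.
- A reader might infer that the groups do differ in prior exposure or tolerance. No passage shows this. The introduction gives insurance cover as a reason for switching, which need not relate to IRR history.
- A reader might combine the weak balance tests with the IRR shift. They concern different variables: a missed imbalance in age does not by itself imply IRR bias. Section 4.9.4 also does not say that good balance means a non-significant test.
- A reader might infer that EDSS is unobtainable for comparators. The schedule in Table 1 covers only the switching group and places PDDS there as well, so the table settles nothing. The mismatch between 4.2 and 4.9.4 is one of wording.

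Section 4.2 does concede limited interpretation, but because IRRs are collected differently in the two groups, not because of infusion history.

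**Conclusion.** The concern holds in a limited form. The statement that confounding is disposed of by balance on demographic and disease variables is wrong, and the primary analysis of a non-randomised comparison should not depend on it. The plan neither looks for nor removes a difference in prior anti-CD20 exposure.

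The documents do not fix the size of the resulting bias. Within the eligible window their own figures give 1.8 points per course, if ocrelizumab rates carry over to rituximab-experienced patients. With 5 to 10% first infusions among comparators it would be 3.2 to 6.4 points in the hiding direction. The assumed-driver scenarios run from 0.6 to 6.8 points. The last two ranges rest on shares, prevalences and relative risks that the documents do not supply. The direction could go either way. The stated aim of estimating relative tolerability, rather than proving superiority, does not help, because a biased estimate defeats that aim too.

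**What to change.** In 4.9.4, make the adjusted GEE or GLMM model primary whatever the balance results, with a fixed covariate list:

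- age;
- sex;
- baseline PDDS;
- number of anti-CD20 infusions before the first analysed infusion;
- months from the last rituximab dose to the first analysed infusion.

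Fix the interval at baseline. A per-infusion interval would have no overlap, because the Day 15 ocrelizumab infusion has no counterpart in comparators treated about six months apart.

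Report the unadjusted result as a sensitivity analysis. Judge balance by standardised differences rather than p-values. Use PDDS in both 4.2 and 4.9.4. Delete the statement that balance removes confounding.

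As a further sensitivity analysis, add prior rituximab IRR and premedication. Prior IRR must be restricted to infusions before the first analysed one. Otherwise, for comparators with retrospective data, the covariate would include the outcome.

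Cost: mostly SAP wording, since dose count and last-dose date are already needed for eligibility. Prior IRRs do need a new provision, because retrospective IRR collection is now described only for comparators and would have to be extended to switchers. Premedication needs some further abstraction. No change to sample size or treatment is involved.
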